- *Cigarette littering message (Control)*: Messages about littering cigarettes will include text designed to discourage people from littering their cigarette butts, and an image related to the message. Each condition has 5 messages that will be repeated 3 times in a counterbalanced order. Study investigators used text developed by

investigators associated with our Center for Regulatory Research on Tobacco Communication. Design of these messages was developed by our team.

Randomization

At the end of the baseline survey, survey software will randomly assign participants to one of the three study arms. Participants will have an equal chance of being randomized to each study arm.

Sample Size

Sample Size Background:

Our study is examining the difference in quit intention for participants that receive 1) Optimal constituent messages with quitline information, and self-efficacy information, or 2) Sub-optimal constituent messages or 3) Messages about littering cigarette butts.

[figure not shown]
No studies from the literature that we could find examined difference in quit intention or quitting behaviors by optimal text vs. sub-optimal warning text vs. control in a warning or smoking communication context.

In a meta-analysis by Noar et al. 2014 (Pictorial cigarette pack warnings: a meta-analysis of experimental studies) the effect size between pictorial vs. text only warnings on intention to quit smoking was $d=0.54$. Other outcomes ranged between effect size $d=-0.03$ (recall of warning text), and $d=1.82$ (intention not to start smoking).

Assumptions for the power calculation:

- The smallest effect size between our groups will be between the optimal and sub-optimal group. If we can see a difference between these groups, we will be able to see the larger effects that we expect between the other groups.
- We will be using a continuous measure of quit intention (or treating quit intention as a continuous variable, and collecting it as a categorical response).
- The effect size on quit intention is likely to be smaller for added self efficacy and quit line text than for added pictorial images.
- To be conservative, we will use a one time measure to calculate power, repeated measures would add power to this analysis (decrease necessary sample size).
- We will use the d statistic to see what group size would have to be enrolled, and compare two means (optimal and sub-optimal) with a t-test

Based on these assumptions:

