Constructs	
 Sex, Sexuality Hispanic Origin, Race Address Education Age Health Household Size Income (above or below FPL) Trust in FDA and CDC Nicotine Dependence (FTND) Previous Quit Attempts Smoking Status Quit Intentions Littering Intention Self Efficacy Response Efficacy Positive and Negative Thoughts (Freq, Degree) Current OTP Use Knowledge of HE and Constituents Tripartite Risk Mental Health (K6) Study Information All Previous Day Behavior Qs 	
Previous day behaviors:
 
 Littering on the ground Littering from Car Forgoing Butting out Number of Cigarettes 
Cognitive Questions:
 
 Thinking about chemicals Thinking about risks Thinking about littering Thinking about quitting Message Negative Affect Message Credibility Perceived Effectiveness 	
 Nicotine Dependence (FTND) Quit Attempts Smoking Status Quitline Awareness Quitline Use Quit Intentions Quitline Intention Littering Intention Self Efficacy Response Efficacy Positive and Negative Thoughts (Freq, Degree) Current OTP Use Knowledge of HE and Constituents Tripartite Risk Credibility of FDA Mental Health (K6) Action Expectancies Reactance Talking about messages All Previous Day Behavior Qs Quality Assurance Questions 	
 Nicotine Dependence (FTND) Quit Attempts Smoking Status Quitline Use Quit Intentions Quitline Intention Littering Intention Self Efficacy Response Efficacy Positive and Negative Thoughts (Freq, Degree) Current OTP Use Knowledge of HE and Constituents Tripartite Risk Mental Health (K6) Action Expectancies All Previous Day Behavior Qs

Statistical Principles

Confidence Intervals and P Values

Level of statistical significance

$\alpha=0.05$

Description and rationale for any adjustment for multiplicity and, if so detailing how the type 1 error is to be controlled

NA

Confidence Intervals to be reported

95% CI

Adherence and Protocol Deviations

Definition of adherence to the intervention and how this is assessed including extent of exposure

Compliance with the protocol is assessed as follows:

- Completion of daily surveys, during which participants view intervention stimuli. % Compliance = number of daily surveys completed / 15 (number of surveys supposed to be completed)*100%
- Completion of post test surveys at post 1 and post 2

Description of how adherence to the intervention will be presented

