- Adherence for the daily surveys will be presented with completion % as well as the mean number complete by treatment group
- Completion of post test surveys will be presented by % completing each by treatment group

Definition of protocol deviations for the trial

- Minor protocol deviation: change in eligibility (ex: turning 66) between screening and baseline
- Minor protocol deviation: completing the wrong sequence of message days due to survey signal error
- Major protocol deviation: No protocol deviations in this trial will impact the safety or physical or mental integrity of the participants in the trial. A slightly older participant, or a participant that receives a slightly different number of messages will both be included as covariates during analysis, so they will not impact the scientific validity of the trial. Therefore, we do not classify any protocol deviations as 'major'

Description of which protocol deviations will be summarized

- Protocol deviations will not be summarized overall, but data related to the deviations will be included in manuscripts. For example, we will not say X participants were older than 65, but will include mean age in a demographic table by treatment group. Similarly, we will not include how many people completed an extra 'day' of the protocol, but we will report the mean number of days participants completed by treatment group.

Analysis Populations

Definition of analysis populations

Outcomes assessed only at post test (including quit intentions) will be analyzed using multiple imputation such that everyone who was randomized will be included in the analysis, and those with missing outcome data will have their outcomes imputed.

For outcomes that were measured daily, all participants that completed at least one of the daily surveys will be included in the planned repeated measure models.

Secondary outcomes may be analyzed using complete case analysis, without imputation.

Trial Population

Screening Data

Screening data will be provided based on the CONSORT guidelines, and CONSORT flow chart will be included with publications.

Eligibility

Minimum Age: 18 Years

Maximum Age: 65 Years

Sex: All

Gender Based: No

Inclusion Criteria:

[figure not shown]
- Have smoked at least 100 cigarettes in his or her lifetime
- Currently smoke cigarettes every day or some days
- Work or home access to the internet
- Email account that is regularly used
- Lives in the US
- Comfortable taking a survey in English

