What analysis method will be used and how treatment effects will be presented

Linear regression for continuous outcomes, logistic for dichotomous.

Any adjustment for covariates

Covariates included for the imputation (in addition to treatment group):

- Dose of ads (# of times participants viewed a message)
- Gender (Male, Female, Other) (The GenIUSS Group, 2014)
- Age (continuous)
- Poverty Status (Above or Below Poverty Line)(Brewer et al., 2018; Department of Health and Human Services, 2017)
- Education (6 categories, same as phone survey)
- FTND Sum Using scoring from Heatherton et al. 1991 (Fagerstrom Test for Nicotine Dependence)(Fagerstrom, Heatherton, & Kozlowski, 1990; Heatherton et al., 1991)

Covariates included in the analysis model (in addition to treatment group):

- Dose of ads (# of times participants viewed a message)

Methods used for assumptions to be checked for statistical methods

For continuous outcomes, we assume the distribution of dependent variable given a predictor variable (intervention) is 1) independent 2) normality 3) constant variance (homogeneity of variance). We can check normality with Q-Q plot of the residual or perform Wilk-Shapiro test and use a scatter plot of residual on predictor variable (intervention) to check independence and constant variance.

Details of alternative methods to be used if distributional assumptions do not hold (eg normality, proportional hazards, etc)

If we have a violation for normality assumption, we can have two options: 1) transform our data so that the shape of our response variable become normally distributed or 2) choose the non-parametric method like Kruskal-Wallis which does not require the assumption of normality. The ANOVA can be considered a robust test against the normality assumption though. If the assumption of homogeneity of variances has been violated, we can use Welch or Brown and Forsythe test. Even though we alternatively perform a Kruskal-Wallis test, in most cases, Welch test is best. We don't expect to have dependency issues in our data.

Any planned sensitivity analyses for each outcome where applicable

Sensitivity analyses may be carried out using a 'complete case analysis' framework

Any planned subgroup analyses for each outcome including how subgroups are defined

None a priori

Missing Data

Multiple imputation will be used so that everyone who was randomized to an intervention will be included in the primary analysis

Additional Analyses

None a priori

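### The main models adjust for dose of ads, which accrues after randomisation, and no regression without it is planned

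*Combined protocol and SAP*

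**What the plan says.** In the SAP, Analysis Methods, Post test measures, continuous outcomes get linear regression and dichotomous outcomes logistic regression. Under "Covariates included in the analysis model (in addition to treatment group", the only entry is "Dose of ads (# of times participants viewed a message". The section on Daily Questionnaire Measures repeats the same single covariate for the mixed models. The primary outcome, the pre-post difference in quit intentions at day 16, is one of the post-test measures.

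On timing, the Randomization section states: "At the end of the baseline survey, survey software will randomly assign participants to one of the three study arms". Adherence and Protocol Deviations measures compliance by "Completion of daily surveys, during which participants view intervention stimuli", as a percentage of 15. Draft Table 1 labels the message count as a follow-up quantity.

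Under Missing Data for the post-test measures: "Multiple imputation will be used so that everyone who was randomized to an intervention will be included in the primary analysis". The only sensitivity analysis there is an optional complete-case analysis, with no mention of dropping dose. The daily measures have no planned sensitivity analysis, and neither section plans additional analyses.

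The definition of protocol deviations gives the reason for the adjustment. Older participants and those with a different number of messages are to be handled as covariates, so that validity is not affected. Yet "Age (continuous" appears only in the imputation list, not in either analysis-model list.

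**The concern.** A covariate that accrues after randomisation can itself be affected by the arm. Dose here closely tracks the number of daily surveys completed, and smokers who are more motivated to quit may complete more of them. If arms differ in completion, comparing participants at equal dose compares people who differ in motivation. If the messages work through repeated exposure, holding exposure fixed also removes part of the effect of assignment. Including everyone randomised through imputation does not restore that effect when the model then conditions on adherence.

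The primary estimate is at stake. The plan will report "completion % as well as the mean number complete by treatment group", which would reveal a gap in dose but not correct the estimate. The plan also relies on this adjustment as its safeguard for validity. The deviation it names is a survey-signal error, but the covariate counts every survey skipped by choice as well.

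**Working it through.** **1. The plan's own figure.** The Sample Size section assumes d = 0.25, 80% power and alpha 0.05, and would "compare two means (optimal and sub-optimal) with a t-test". Two-sided, n = 2(1.960 + 0.842)²/0.25² = 251.2, so 252 per group. The t-test solution is 252.1, so 253, which matches the plan. Power is 80.1% at 253 per arm and 82.2% at 267 (800/3 = 266.7). That test has no dose term.

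**2. What dose adjustment does in a linear model.**

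arm coefficient with dose = arm coefficient without dose − γ × Δ

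Here γ is the within-arm slope of outcome on dose and Δ is the difference in mean dose between arms. The shift is zero if either is zero. The documents give neither, so everything in steps 3 to 7 is assumed.

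**3. Primary outcome, illustration.** Assume no true arm effect, mean dose about 12 of 15 with SD about 2.4, and 267 per arm. An unmeasured motivation score predicts change in quit intentions by 0.15 to 0.30 SD per SD and correlates with dose at 0.34, 0.47 or 0.68. Then γ ≈ slope × correlation / 2.40. For slope 0.30, correlation 0.34 and gap 0.86, the shift is 0.30 × 0.34/2.40 × 0.86 = 0.037 SD. Simulation with 1,000,000 per arm, which respects the 0-15 limits, gives 0.035.

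For type I error, SE ≈ √(2/266.7) = 0.0866, so a shift of 0.035 is 0.40 SE. P(Z > 1.56) + P(Z < −2.36) ≈ 0.060 + 0.009 = 6.9%. Simulated absolute shifts, in SD of change, for slopes 0.15 to 0.30:

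| Motivation-dose correlation | Gap 0.42 | Gap 0.86 | Type I error over both gaps |
|---|---|---|---|
| 0.34 | 0.009-0.017 | 0.017-0.035 | 5.1-6.9% |
| 0.47 | 0.012-0.025 | 0.025-0.050 | 5.2-8.8% |
| 0.68 | 0.017-0.035 | 0.036-0.071 | 5.5-13.0% |

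With balanced dose, or with motivation unrelated to change and no effect of dose itself, the shift is about 0. At a gap of 0.2 it is at most 0.017 SD (5.5%). Estimates on arm alone stay within 0.003 of zero.

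For scale against d = 0.25: with pre-post correlation 0.5 the SD of change is √(2 × 0.5) = 1 raw SD, so 0.035 and 0.071 are 14% and 28% of d. With correlation 0.7 it is √(2 × 0.3) = 0.775, giving 11% and 22%.

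**4. If dose has a real effect.** If each message moves the outcome by 0.02 to 0.04 SD, adjustment removes between 0.02 × 0.42 = 0.008 and 0.04 × 0.86 = 0.034 SD of the effect of assignment.

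**5. Daily models.** The plan does not say whether dose is the total or the count to date. At gaps of 0.42 to 0.90, total dose gives shifts of 0.007-0.031 SD (correlation 0.32, type I error 5-7%) to 0.014-0.062 SD (0.68, 5.5-14%). Count to date gives at most 0.009 SD (5.2%).

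**6. Dichotomous outcomes.** With a motivation slope of 0.5 to 1.0 log-odds per SD, the null odds ratio is multiplied by 1.03-1.10 at correlation 0.34 (type I error 5-8%) and by 1.06-1.23 at 0.68 (6-20%).

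**7. Dose in the imputation model.** With 16% missing in one arm and 19-22% in the other, depending on dose, imputing on arm and dose and then analysing arm alone stays within 0.004 SD of zero. Keeping dose in the analysis gives 0.009-0.069 SD. Leaving dose out of the imputation as well gives up to 0.011 SD. Dose therefore belongs in the imputation model.

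**The case against.** The strongest reply is that the harm is conditional and the design points to a small gap. Reminders, payments and bonuses are the same in all arms, and participants are not told about the possible interventions. The powered contrast is between two arms that differ only in FDA source and quit information. With SD 2.4 and 267 per arm, the SE of a dose gap is 2.4 × √(2/267) = 0.21 messages. Gaps of 0.42 to 0.86 thus assume a systematic difference of about 2 to 4 SE, and the top of each range combines the largest gap, slope and correlation. All of this stands: the figures illustrate a mechanism and are not predictions, and the gap for optimal against sub-optimal may well be near zero. It does not carry over to constituent against littering messages. That contrast is also a stated hypothesis, and the content differs enough that equal completion cannot be presumed.

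Four narrower points also have force:

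- **Daily models.** If dose is the count to date, the effect is negligible. The Draft Table 1 label suggests the total but does not define the model term.
- **Logistic models.** With balanced dose the change in the odds ratio is only the usual conditional-against-marginal difference (1.42 against 1.41, or 1.44 against 1.40), so it adds little.
- **Age.** The wording on age may be loose, and age precedes randomisation, so it is a matter of consistency only.
- **Complete-case analysis.** Secondary outcomes may be analysed on complete cases. There an arm-only model can still be off by about 0.012 SD under the missingness assumed in step 7, so dropping dose helps but does not make those estimates exact.

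The Kruskal-Wallis, Welch and Brown-Forsythe fallbacks list no covariate, but they apply only if assumptions fail.

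**Conclusion.** The concern holds. As written, the primary regression and the daily mixed models condition on a post-randomisation measure of adherence, and no planned regression avoids it. That follows from the text alone. The consequence is not known from the documents: zero if dose is balanced across arms or unrelated to outcome within arm, and otherwise of unknown size and either sign. For the primary outcome, the illustrated range is 0.009 to 0.071 SD of change at gaps of 0.42 to 0.86 messages, and at most 0.017 SD at a gap of 0.2. A model without dose estimates the effect of assignment whether or not dose is balanced, so nothing is gained by taking the risk. This should be fixed; it does not undermine the design.

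**What to change.** Remove dose of ads from the analysis models for the post-test and daily outcomes, and estimate the effect of randomised arm. Keep dose in the imputation model and in the adherence reporting by arm. Label any dose-adjusted model exploratory, and state whether its dose is the total or the count to date. Rewrite the protocol-deviation sentence that relies on covariate adjustment for validity, and reconcile what it says about age with the analysis-model lists.

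Optional, for precision only: adjust for the baseline value where a pre-test item exists (quit intentions, self efficacy, response efficacy, previous-day behaviours). Quitline intention has a pre-test variable name in Appendix A but is not in the pre-test construct tables, so check that it was collected. For quit intentions the pre-post difference can stay as the outcome. With the pre-test score in the model, the arm coefficient is the same for the difference and for the post-test score.

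The cost is a dated SAP amendment. No new data are needed and the stated power is unaffected. The amendment should say whether outcomes by arm had been seen, because the final dataset named in the SAP References is dated 07232018, one day before SAP version 1 (July 24, 2018).

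### The SAP's assumption-check fallbacks can replace the primary regression with three-arm omnibus tests that do not answer optimal versus sub-optimal, and no result is designated primary

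*Combined protocol and SAP*

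**What the plan says.** The SAP's Post test measures section gives the method as "Linear regression for continuous outcomes, logistic for dichotomous", with treatment group and dose of ads in the model. It names no reference arm, coefficient or contrast.

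The check is described as "We can check normality with Q-Q plot of the residual or perform Wilk-Shapiro test", with no threshold for either. The fallback then begins "If we have a violation for normality assumption, we can have two options". The first option is to "transform our data so that the shape of our response variable become normally distributed", and no transformation is named. The second is to "choose the non-parametric method like Kruskal-Wallis which does not require the assumption of normality". The next remark points the other way: "The ANOVA can be considered a robust test against the normality assumption though". On variances the SAP says "If the assumption of homogeneity of variances has been violated, we can use Welch or Brown and Forsythe test", and adds "Even though we alternatively perform a Kruskal-Wallis test, in most cases, Welch test is best". Nothing says which result is primary if these differ.

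The comparisons of interest are stated elsewhere. The SAP Objectives give two directional hypotheses: constituent messages above littering, and messages with FDA source and quit information above messages without it. The protocol's Study Methods hypothesis puts optimal above both sub-optimal and control. The Sample Size section sizes the trial on a t-test of optimal versus sub-optimal. Confidence Intervals and P Values calls for 95% CIs, and missing primary outcomes are to be multiply imputed.

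**The concern.** The hypotheses are directional and concern particular arms. Run across three arms, Kruskal-Wallis, Welch and Brown-Forsythe ask only whether the arms differ somewhere. If such a test took the place of the regression, the primary p-value would not say which arm was better, and two analysts following the same text could report different primary results.

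The fallbacks also fit poorly with the rest of the SAP. As named, they leave out the dose covariate. No way of pooling them over the imputed datasets is stated. The three-arm versions give no mean difference with a 95% CI.

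The occasion for a switch is likely to arise, because the primary score is a coarse average of three 4-point items and a formal normality test will usually reject it.

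**Working it through.** **1. The plan's own figure.** Inputs from Sample Size and Statistical Principles: d = 0.25, 80% power, alpha 0.05. Sidedness is not stated; I take two-sided.

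n per group = 2(z₀.₉₇₅ + z₀.₈₀)²/d² = 2(1.960 + 0.842)²/0.0625 ≈ 251.2, so 252 by the normal approximation. The t-based solution is 252.1, rounded up to 253, and 3 × 253 = 759. The stated figures reproduce, and they rest on a two-group contrast. With 800 enrolled, 800/3 ≈ 267 per arm, and that contrast has 82.2% power.

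**2. Shape of the primary score.** The sum of three items scored 1 to 4 runs from 3 to 12, so the average takes 10 values. The pre/post difference of sums runs from −9 to 9, so it takes 19. Neither can be normal. A one-to-one transformation of 10 values still has 10 values.

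**3. What a three-arm test responds to.** For the F test, λ = n Σ(μᵢ − μ̄)², with 2 and 3n − 3 = 798 degrees of freedom at n = 267. Means are in SD units. This step needs no assumption about item distributions.

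| Optimal, sub-optimal, littering | Σ(μᵢ − μ̄)² | λ | Rejects |
|---|---|---|---|
| 0.25, 0.25, 0 | 0.0417 | 11.125 | 85.5% |
| 0.25, 0, 0 | 0.0417 | 11.125 | 85.5% |
| 0, 0.25, 0 | 0.0417 | 11.125 | 85.5% |

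The three rows are the same to the test. In the first, the FDA source adds nothing; in the third, it does harm.

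**4. The same on scores like the primary one.** These are simulations on assumed inputs that are not in the documents: three 4-point items with loading 0.8; symmetric, floor-skewed and ceiling-skewed cut-points; latent pre/post correlation 0.6 (0.4 to 0.8 under the null); dose Binomial(15, 0.8) in every arm; 267 per arm; 2,000 trials per cell; change score. The shifts gave an observed d of 0.19 to 0.22.

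- Shapiro-Wilk on the residuals rejects in 70–100% of null trials and in 51–100% when arms differ.
- With optimal equal to sub-optimal and both above littering, Kruskal-Wallis is significant in 61–72% and Welch in 62–73%. The optimal-versus-sub-optimal regression contrast is significant in 4.8–5.1%.
- With only one arm better, Kruskal-Wallis is significant in 60–72% if that arm is optimal and 60–71% if it is sub-optimal. The contrast significantly favours optimal in 61–72% and 0.0%.

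**5. Power for constituent versus littering.** Take d = 0.20 for both constituent arms and normal data.

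- One constituent arm against littering: SE = √(2/267) = 0.0865, 0.20/0.0865 = 2.31, power 63.6%.
- Three-arm F: λ = 267 × 0.0267 = 7.12, power 66.2%.
- Both constituent arms pooled against littering: SE = √(1/267 + 1/534) = 0.0750, 0.20/0.0750 = 2.67, power 76.0%.

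The omnibus test loses 76.0 − 66.2 = 9.8 points against the pooled contrast, and nothing against the single-arm contrast.

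**6. Whether the regression needs replacing.** In the simulations of step 4, null type I error for optimal versus sub-optimal is 4.0–5.6% with ordinary errors and 3.9–5.4% with robust (HC3) errors. With the message arms' SD at 1.24 times control, ordinary errors give 6.5–6.7% and robust errors 4.8–5.3%. Power for optimal versus sub-optimal at about 0.2 SD is 61–72% with either.

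**The case against.** The strongest reply is that the text is permissive. It lists the Q-Q plot first, makes the formal test optional, says only what can be done, and calls ANOVA robust. Keeping the regression is open. That stands: the Shapiro-Wilk rates show how often a formal test would flag a violation, not how often the method would be switched, which is unknown.

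A reader might infer that the plan never names its comparisons. It does, in the Objectives and Sample Size sections, and a regression on treatment group yields arm coefficients. The gap is that the analysis section does not connect them.

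A reader might also infer a raised false-positive rate from 61–72% set beside about 5%. That is wrong. When littering differs from both constituent arms, an omnibus rejection is correct. Harm arises only if the authors switch, run the test on three arms, and then read significance as optimal beating sub-optimal. The documents do not say they would take that last step. But they define no follow-up comparison either, so the three-arm result alone would leave the hypothesis unanswered.

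Two further points stand. A Welch test on the named pair is not excluded, and it would give a mean difference with a CI. A variance remedy also has a real purpose, since ordinary errors drift to 6.5–6.7% in step 6. Robust errors meet the same need while keeping the covariate and the contrast.

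**Conclusion.** The concern holds as a defect in the analysis section that should be corrected. The SAP allows, without requiring, its primary regression to be replaced by an unnamed transformation or by tests that, across three arms, address a different question. It has no trigger threshold and no statement of which result is primary. The size is best shown by the 85.5% rejection rate in all three configurations of step 3, which rests only on normal data with equal variances, d = 0.25 and 267 per arm. The simulated figures depend on assumed item distributions, equal dose distributions across arms and no missing data; they support the direction, not exact values.

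A general loss of power is not shown. The loss of about 10 points at d = 0.20 applies only if the two constituent arms are pooled against littering, which the SAP leaves undecided; with each arm compared separately there is none. Nor do the documents show that the authors would switch.

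**What to change.** For the primary outcome, replace the normality- and variance-triggered alternatives with a statement that linear regression with heteroscedasticity-robust standard errors is primary whatever the residual shape or variances. Then:

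- Name the contrasts: optimal versus sub-optimal, and constituent versus littering. For the second, say whether the two constituent arms are pooled or each is compared with littering; the protocol hypothesis speaks of optimal against control, the SAP Objectives of constituent messages against control.
- Report each as a mean difference on the 1–4 scale with a 95% CI pooled over the imputations.
- Label any transformed, rank or omnibus analysis as sensitivity only.

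The cost is SAP wording, with almost no power lost to robust errors in step 6. The downside is that a mean difference is reported even when the score is skewed.
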